15.4 Methods for Evaluation of Measurable Disease

All measurements should be taken and recorded in metric notation using a ruler or calipers. All baseline evaluations should be performed as closely as possible to the beginning of treatment and

never more than 4 weeks before the beginning of the treatment.

The same method of assessment and the same technique should be used to characterize each identified and reported lesion at baseline and during follow-up. Imaging-based evaluation is preferred to evaluation by clinical examination unless the lesion(s) being followed cannot be imaged but are assessable by clinical exam.

Clinical lesions: Clinical lesions will only be considered measurable when they are superficial (e.g., skin nodules and palpable lymph nodes) and ≥ 10 mm diameter as assessed using calipers (e.g., skin nodules). In the case of skin lesions, documentation by color photography, including a ruler to estimate the size of the lesion, is recommended.

Chest x-ray: Lesions on chest x-ray are acceptable as measurable lesions when they are clearly defined and surrounded by aerated lung. However, CT is preferable.

Conventional CT and MRI: This guideline has defined measurability of lesions on CT scan based on the assumption that CT slice thickness is 5 mm or less. If CT scans have slice thickness greater than 5 mm, the minimum size for a measurable lesion should be twice the slice thickness. MRI is also acceptable in certain situations (e.g., for body scans).

Use of MRI remains a complex issue. MRI has excellent contrast, spatial, and temporal resolution; however, there are many image acquisition variables involved in MRI, which greatly impact image quality, lesion conspicuity, and measurement. Furthermore, the availability of MRI is variable globally. As with CT, if an MRI is performed, the technical specifications of the scanning sequences used should be optimized for the evaluation of the type and site of disease. Furthermore, as with CT, the modality used at follow-up should be the same as was used at baseline and the lesions should be measured/assessed on the same pulse sequence. It is beyond the scope of the RECIST guidelines to prescribe specific MRI pulse sequence parameters for all scanners, body parts, and diseases. Ideally, the same type of scanner should be used and the image acquisition protocol should be followed as closely as possible to prior scans. Body scans should be performed with breath-hold scanning techniques, if possible.

PET-CT: At present, the low dose or attenuation correction CT portion of a combined PET-CT is not always of optimal diagnostic CT quality for use with RECIST measurements. However, if the site can document that the CT performed as part of a PET-CT is of identical diagnostic quality to a diagnostic CT (with IV and oral contrast), then the CT portion of the PET-CT can be used for RECIST measurements and can be used interchangeably with conventional CT in accurately measuring cancer lesions over time. Note, however, that the PET portion of the CT introduces additional data which may bias an investigator if it is not routinely or serially performed.

Ultrasound: Ultrasound is not useful in assessment of lesion size and should not be used as a method of measurement. Ultrasound examinations cannot be reproduced in their entirety for independent review at a later date and, because they are operator dependent, it cannot be guaranteed that the same technique and measurements will be taken from one assessment to the

next. If new lesions are identified by ultrasound in the course of the study, confirmation by CT or MRI is advised. If there is concern about radiation exposure at CT, MRI may be used instead of CT in selected instances.

Endoscopy/Laparoscopy: The utilization of these techniques for objective tumor evaluation is not advised. However, such techniques may be useful to confirm complete pathological response when biopsies are obtained or to determine relapse in trials where recurrence following complete response (CR) or surgical resection is an endpoint.

Tumor markers: Tumor markers alone cannot be used to assess response. If markers are initially above the upper normal limit, they must normalize for a patient to be considered in complete clinical response.

Cytology/Histology: These techniques can be used to differentiate between partial responses (PR) and complete responses (CR) in rare cases (e.g., residual lesions in tumor types, such as germ cell tumors, where known residual benign tumors can remain).

The cytological confirmation of the neoplastic origin of any effusion that appears or worsens during treatment when the measurable tumor has met criteria for response or stable disease is mandatory to differentiate between response or stable disease (an effusion may be a side effect of the treatment) and progressive disease.

FDG-PET: While FDG-PET response assessments need additional study, it is sometimes reasonable to incorporate the use of FDG-PET scanning to complement CT scanning in assessment of progression (particularly possible 'new' disease). New lesions on the basis of FDG-PET imaging can be identified according to the following algorithm:

- Negative FDG-PET at baseline, with a positive FDG-PET at follow-up is a sign of PD based on a new lesion.
- No FDG-PET at baseline and a positive FDG-PET at follow-up: If the positive FDG-PET at follow-up corresponds to a new site of disease confirmed by CT, this is PD. If the positive FDG-PET at follow-up is not confirmed as a new site of disease on CT, additional follow-up CT scans are needed to determine if there is truly progression occurring at that site (if so, the date of PD will be the date of the initial abnormal FDG-PET scan). If the positive FDG-PET at follow-up corresponds to a pre-existing site of disease on CT that is not progressing on the basis of the anatomic images, this is not PD.
- FDG-PET may be used to upgrade a response to a CR in a manner similar to a biopsy in cases where a residual radiographic abnormality is thought to represent fibrosis or scarring. The use of FDG-PET in this circumstance should be prospectively described in the protocol and supported by disease-specific medical literature for the indication. However, it must be acknowledged that both approaches may lead to false positive CR due to limitations of FDG-PET and biopsy resolution/sensitivity.

Note: A 'positive' FDG-PET scan lesion means one which is FDG avid with an uptake greater than twice that of the surrounding tissue on the attenuation corrected image.

15.5 Response Criteria

15.5.1 Evaluation of Target Lesions

Complete Response (CR): Disappearance of all target lesions. Any pathological lymph nodes (whether target or non-target) must have reduction in short axis to <10 mm.

Partial Response (PR): At least a 30% decrease in the sum of the diameters of target lesions, taking as reference the baseline sum diameters.

Progressive Disease (PD): At least a 20% increase in the sum of the diameters of target lesions, taking as reference the smallest sum on study (this includes the baseline sum if that is the smallest on study). In addition to the relative increase of 20%, the sum must also demonstrate an absolute increase of at least 5 mm. (Note: the appearance of one or more new lesions is also considered progressions).

Stable Disease (SD): Neither sufficient shrinkage to qualify for PR nor sufficient increase to qualify for PD, taking as reference the smallest sum diameters while on study.

15.5.2 Evaluation of Non-Target Lesions

Complete Response (CR): Disappearance of all non-target lesions and normalization of tumor marker level. All lymph nodes must be non-pathological in size (<10 mm short axis).

Note: If tumor markers are initially above the upper normal limit, they must normalize for a patient to be considered in complete clinical response.

Non-CR/Non-PD: Persistence of one or more non-target lesion(s) and/or maintenance of tumor marker level above the normal limits.

Progressive Disease (PD): Appearance of one or more new lesions and/or unequivocal progression of existing non-target lesions. Unequivocal progression should not normally trump target lesion status. It must be representative of overall disease status change, not a single lesion increase. Although a clear progression of “non-target” lesions only is exceptional, the opinion of the treating physician should prevail in such circumstances, and the progression status should be confirmed at a later time by the review panel (or Principal Investigator).

15.5.3 Evaluation of Best Overall Response

The best overall response is the best response recorded from the start of the treatment until disease progression/recurrence (taking as reference for progressive disease the smallest measurements recorded since the treatment started). The patient's best response assignment will depend on the achievement of both measurement and confirmation criteria.

Table 8. Response Criteria for Patients with Measurable Disease (e.g., Target Disease)

| Target Lesions | Non-Target Lesions | New Lesions | Overall Response | Best Overall Response when Confirmation is Required* |
|-----------------------|-----------------------------|--------------------|-------------------------|---|
| CR | CR | No | CR | ≥ 4 wks. Confirmation** |
| CR | Non-CR/Non-PD | No | PR | ≥ 4 wks. Confirmation** |
| CR | Not evaluated | No | PR | |
| PR | Non-CR/Non-PD/not evaluated | No | PR | |
| SD | Non-CR/Non-PD/not evaluated | No | SD | documented at least once ≥ 4 wks. from baseline** |
| PD | Any | Yes or No | PD | no prior SD, PR or CR |
| Any | PD*** | Yes or No | PD | |
| Any | Any | Yes | PD | |

* See RECIST 1.1 manuscript for further details on what is evidence of a new lesion.
 ** Only for non-randomized trials with response as primary endpoint.
 *** In exceptional circumstances, unequivocal progression in non-target lesions may be accepted as disease progression.

Note: Patients with a global deterioration of health status requiring discontinuation of treatment without objective evidence of disease progression at that time should be reported as “symptomatic deterioration.” Every effort should be made to document the objective progression even after discontinuation of treatment.

For Patients with Non-Measurable Disease (e.g., Non-Target Disease)

| Non-Target Lesions | New Lesions | Overall Response |
|---------------------------|--------------------|-------------------------|
| CR | No | CR |
| Non-CR/non-PD | No | Non-CR/non-PD* |
| Not all evaluated | No | not evaluated |
| Unequivocal PD | Yes or No | PD |
| Any | Yes | PD |

* ‘Non-CR/non-PD’ is preferred over ‘stable disease’ for non-target disease since SD is increasingly used as an endpoint for assessment of efficacy in some trials so to assign this category when no lesions can be measured is not advised

15.6 Duration of Response

Duration of overall response: The duration of overall response is measured from the time

measurement criteria are met for CR or PR (whichever is first recorded) until the first date that recurrent or progressive disease is objectively documented (taking as reference for progressive disease the smallest measurements recorded since the treatment started).

The duration of overall CR is measured from the time measurement criteria are first met for CR until the first date that progressive disease is objectively documented.

Duration of stable disease: Stable disease is measured from the start of the treatment until the criteria for progression are met, taking as reference the smallest measurements recorded since the treatment started, including the baseline measurements.

15.7 Progression-Free Survival

PFS is defined as the duration of time from start of treatment to time of progression or death, whichever occurs first.

15.8 Response Review

All responses will be reviewed by an expert independent of the study at the study's completion. All imaging will be stored at Columbia University Irving Medical Center

15.9 Unblinding Procedures

Not applicable

15.10 Stopping Rules

Not applicable

16. DATA REPORTING / REGULATORY REQUIREMENTS

Adverse event lists, guidelines, and instructions for AE reporting can be found in Section 10.0 (Adverse Events: List and Reporting Requirements).

16.1 Data Collection

The Herbert Irving Comprehensive Cancer Center has an electronic clinical trials and data management system (CTMS) that will be used for data collection. CRFs for the study will be built into the CTMS for data entry. The system has full auditing capabilities which is web-based and housed on a server in a fully HIPAA compliant server room with restricted access and video camera monitoring. All users must login with their own application username and password. Users off campus must first access the Virtual Private Network with their assigned campus username and password and then use their application credentials. Users are only able to see study information if they are indicated as study personnel in our electronic IRB system. Users are limited to access based on the role assigned in their corresponding protocol. Subject data is entered directly into the system, which (in the case of Columbia subjects) confirms the correct identity of patients via an interface with the electronic medical patient index. Staff with the

appropriate IRB defined roles can run reports within the system for reporting purposes.

16.2 Data Reporting

Case Report Forms will be completed for each subject enrolled into the clinical study through the CTMS. It is the investigator's responsibility for ensuring that all clinical and laboratory data entered on the corresponding CRFs are complete, accurate and authentic.

16.3 Data and Safety Monitoring Committee

The NCI-approved Data Safety and Monitoring Committee (DSMC) of the Herbert Irving Comprehensive Cancer Center (HICCC) will monitor every subject who receives treatment on this protocol for toxicity. This protocol will adhere to the policies of the currently approved HICCC Data and Safety Monitoring Plan (DSMP), which is in accordance with NCI and CUMC-IRB policy and guidelines. The committee is chair is appointed by the HICCC Director. The committee consists of HICCC faculty and staff with expertise in oncology, research pharmacy, research nursing, and data management. The DSMC convenes twice a month to review patient safety and the conduct of the trial. The PI will submit data and safety monitoring reports to the DSMC at a frequency to be determined by the DSMC based on risk to the subjects.

At the time of renewal, the study team will submit the most recent DSMC approval letter for safety review to the CUMC IRB. Any modifications that are required by the DSMC to ensure patient safety will be submitted to the IRB. All protocol deviations, violations, and eligibility waivers will be submitted to and approved by the DSMC prior to being reported to the IRB. All study data reviewed and discussed during these meetings will be kept confidential.

For multicenter research, the principal investigator will assure that there is a mechanism in place to distribute the report to all participating investigators for submission to their local IRB. The report will document that a review of data and outcomes across all centers took place on a given date. It will summarize the DSMC's review of the cumulative toxicities reported from all participating sites without specific disclosure by treatment arm. It will also inform site investigators of the study the DSMC's conclusion with respect to progress or need for modification of the protocol.

16.4 Quality Control and Quality Assurance

Independent monitoring of the clinical study for protocol and GCP compliance will be conducted periodically by the CPDM Compliance Core on behalf of the HICCC DSMC. Additionally, the Compliance Oversight Committee of the IRB at Columbia University Medical Center may audit the study at any time per institutional policies and procedures. The investigator-sponsor and Columbia University Medical Center will permit direct access of the study monitors and appropriate regulatory authorities to the study data and to the corresponding source data and documents to verify the accuracy of this data.

A risk-based approach will be used by the Compliance Core to determine the frequency, number of subject charts, and data elements to be monitored. The Compliance Coordinator will review the study status and summarize enrollment, toxicities, SAEs/UPs, statistical endpoints (e.g., stopping

rules), etc. for the full DSMC membership at the regularly scheduled meetings.

Internal On-site Monitoring:

- Initial, recurrent, and close-out on-site monitoring visits will also be conducted at remote clinical sites, as appropriate/feasible. Other sites will have monitoring performed remotely (see below for further details).
 - The study Monitoring Visit Log will be completed and signed by the monitor and the PI/CRNP/CRN and/or CRC and will be filed in the regulatory binder.
- The Compliance Coordinator will communicate with the site coordinator/Site Principle Investigator to schedule the monitoring visit and arrange for access to study materials and documentation.
- The assigned Compliance Coordinator will monitor IIT trials within 1 month after the first subject is enrolled and throughout the life of the study to ensure that the study is being conducted in accordance with the protocol, GCP, applicable federal and local regulations, and per all applicable SOPs. The Compliance Coordinator is responsible to notify the PI and CRNP/CRN/CRC of upcoming monitor visits and convey what information and documentation will be required for the visit(s). The Compliance Coordinator is responsible for verifying that informed consent is properly obtained, eligibility is met (via the central registration process), and all study procedures are conducted according to the study protocol. The Compliance Coordinator will also verify that the data reported in the CRF's accurately reflect source documents, that all toxicities have been reported to date, and that all SAE's/UPs/deviations/violations have been reported according to local IRB and HICCC DSMC requirements. The Compliance Coordinator will issue queries and ensure resolution in a timely and efficient manner. The Compliance Coordinator will also monitor for applicable regulatory compliance and research pharmacy compliance (if applicable) and communicate any deficiencies as appropriate.

16.5 Confidentiality

Information about study subjects will be kept confidential and managed according to the requirements of the Health Insurance Portability and Accountability Act (HIPAA). Those regulations require a signed subject authorization informing the subject of the following:

- What protected health information (PHI) will be collected from subjects in this study
- Who will have access to that information and why
- Who will use or disclose that information
- The rights of a research subject to revoke their authorization for use of their PHI.

In the event that a subject revokes authorization to collect or use PHI, the investigator, by regulation, retains the ability to use all information collected prior to the revocation of subject

authorization. For subjects that have revoked authorization to collect or use PHI, attempts should be made to obtain permission to collect at least vital status (e.g., that the subject is alive) at the end of their scheduled study period.

The subject binders will be maintained with in the CPDM offices, a secured floor within the Herbert Irving Pavilion and only the investigator and study staff will have access to the file.

16.6 Source Documents

Source data is all information, original records of clinical findings, observations, or other activities in a clinical trial necessary for the reconstruction and evaluation of the trial. Source data are contained in source documents Examples of these original documents, and data records include: hospital records, clinical and office charts, laboratory notes, memoranda, subjects' diaries or evaluation checklists, pharmacy dispensing records, recorded data from automated instruments, copies or transcriptions certified after verification as being accurate and complete, microfiches, photographic negatives, microfilm or magnetic media, x-rays, subject files, and records kept at the pharmacy, at the laboratories, and at medico-technical departments involved in the clinical trial.

16.7 Case Report Forms

The study case report form (CRF) is the primary data collection instrument for the study. All data requested on the CRF must be recorded. All missing data must be explained. If a space on the CRF is left blank because the procedure was not done or the question was not asked, write "N/D". If the item is not applicable to the individual case, write "N/A".

16.8 Records Retention

Records relating to a specific research activity, including research records collected by investigators, must be maintained for at least three years after completion of the research (45 CFR 46.115(b); 21 CFR 56.115(b); 21 CFR 312.62). This minimum retention period applies whether or not any subjects were enrolled in the study.

If the research is FDA regulated, records should be retained for at least two years after approval of the investigational agent by FDA; if it is not approved, records should be retained at least two years after the study is terminated and FDA is notified (note the additional requirement below for clinical research studies);

Clinical records, including consent forms that document clinical intervention or clinical diagnostic procedure research-related procedures, must be retained in medical records by the institution for at least seven years, per CUMC and NYP policy which is based on state law.

17. STATISTICAL CONSIDERATIONS

17.1 Study Design and Sample Size

This is a multi-center, non-randomized, open-label phase 2 trial to evaluate the efficacy and safety of ruxolitinib in post-transplant patients with advanced cutaneous squamous cell carcinoma. The primary endpoint is overall response rate, defined as the best response confirmed

within the 24 weeks of the start of study therapy.

We will use a Simon Two-Stage Min-Max design with a target overall response rate of 20% (alternative hypothesis), compared to a historical response rate of 5% (null hypothesis) with chemotherapy, with one-sided probability of a type I error set at 0.10 and power of 90%. In the first stage, 18 patients will be accrued. If less than 1 patient achieves a response among the initial 18 patients, the study will be declared negative and terminated. If at least 1 patient achieves a response, an additional 14 patients will be accrued to the second stage for a total of 32 evaluable patients. Overall, if 4 or fewer responses are seen, the study will be declared negative. If at least 5 total patients achieve a response, that treatment will be declared positive for attaining the primary endpoint. There is a 40% chance of stopping at Stage 1 if the true confirmed response rate is at most 5% (null hypothesis). Accounting for 10% dropout, we will plan to enroll a total of 35 patients unless a second safety lead-in is required, in which case the the maximum potential accrual will be 41 patients.

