| Reference therapy | Historical response rates to chemotherapy in advanced cutaneous squamous cell carcinoma in transplant recipients (reference response rate 5-10%) |
| Statistical Methodology | 
Definition of primary outcome/endpoint: The primary endpoint is the overall response rate as defined as the best response, confirmed at ≥ 4 weeks, within the first 24 weeks of the start of study therapy, using RECIST v1.1 criteria.
 
Definition of secondary outcomes/endpoints: PFS is defined as time from registration to time of clinical or radiographic disease progression as defined by RECIST v1.1 criteria, or death. OS is defined as time from registration to time of death from any cause.
 
Analytic plan for primary objective: We will estimate the response rate to ruxolitinib using the exact 95% confidence interval based on the binomial distribution.
 
Analytic plan for secondary and exploratory objectives:
 
• We will estimate the survival distribution for both PFS and OS endpoints using the Kaplan Meier method. The log rank test will be used to examine differences between survival curves.• For correlative studies we will apply either the Fisher's exact test or Wilcoxon rank sum test to examine the correlation between response status and markers for categorical and continuous variables, respectively. 
Sample size justification: We will utilize a Simon mini-max two-stage design in which a 5% RR is considered not promising, a 20% RR is considered promising, and the probabilities of a type I error (falsely accepting a non-promising therapy) and type II error (falsely rejecting a promising therapy) are set at 0.10 and 0.10, respectively. Eighteen patients with advanced cSCC will be accrued in the first stage. If 1 or more patients achieve a response, then an additional 14 will be accrued. If 4 or fewer responses are seen, the study will be declared negative.
 |

Protocol Schema:

[figure not shown]

Table of Contents

| | | |
|-----|---|----|
| 1. | Protocol Signature Page | 3 |
| 1. | Introduction..... | 12 |
| 2. | Study Objectives | 12 |
| 2.1 | Primary Objective | 12 |
| 2.2 | Secondary Objectives..... | 12 |
| 2.3 | Exploratory Objectives | 13 |
| 3. | Background | 13 |
| 3.1 | Cutaneous Squamous Cell Carcinoma | 13 |
| 3.2 | Rationale for JAK inhibition in advanced cutaneous squamous cell carcinoma..... | 13 |

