5.2 Number of Patients

Utilizing a Simon Two-Stage Mini-Max design, 18 patients with advanced cSCC will be accrued in the first stage. If 1 or more patients achieve a response, then an additional 14 will be accrued. If 3 or fewer responses are seen, the study will be declared negative. If the initial safety lead-in does not result in advancement to stage I, an additional 6 patients will need to be accrued for a second safety lead-in. Assuming a 10% drop-out rate, we anticipate a total accrual of 35 patients with a maximum potential accrual of 41 patients (see Statistical Considerations).

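### The final boundary in Section 17.1 and the synopsis (4 or fewer of 32 is negative) gives 79% power, not the stated 90%, and contradicts Section 5.2 (3 or fewer)

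*Combined protocol and SAP*

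**What the plan says.** Three places describe the same two-stage design: 18 patients, stop if there are no responses, otherwise 14 more for a total of 32. They do not share a final rule.

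- **Section 17.1 (Study Design and Sample Size):** "Overall, if 4 or fewer responses are seen, the study will be declared negative". The next sentence makes at least 5 responders the criterion for a positive result.
- **Synopsis, Statistical Methodology:** "If 4 or fewer responses are seen, the study will be declared negative".
- **Section 5.2 (Number of Patients):** "If 3 or fewer responses are seen, the study will be declared negative". This section refers the reader to the statistical section, which gives the other rule.

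Section 17.1 introduces the design with "We will use a Simon Two-Stage Min-Max design". It sets the null response rate at 5% and the target at 20%, "with one-sided probability of a type I error set at 0.10 and power of 90" percent. The synopsis gives the same two rates and the same error limits: the type I error and the "type II error (falsely rejecting a promising therapy) are set at 0.10 and 0.10, respectively". Section 17.1 also states a 40% chance of stopping at stage 1 under the null.

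**The concern.** The sample size, the stage 1 rule and the hypotheses are the same in all three places. Two different final boundaries cannot both give the stated error rates, and a result of exactly 4 responses in 32 (12.5%) is classified in opposite ways.

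In a single-arm, open-label trial the pre-specified boundary is the main protection against choosing the conclusion after seeing the data. If 4 responses occur, either reading could be defended from the protocol and either would look chosen afterwards. If Section 17.1 is followed, the trial also runs about twice the stated risk of discarding a drug that truly has the target response rate.

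**Working it through.** **Inputs** (Section 17.1; rates and error limits also in the synopsis): p0 = 0.05, p1 = 0.20, one-sided type I error at most 0.10, power at least 0.90, n1 = 18, stop if 0 responses, n = 32. The final boundary r (negative if r or fewer) is 4 in Section 17.1 and the synopsis, and 3 in Section 5.2.

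**Formula.** The trial is positive if stage 1 has at least one response and the total exceeds r:

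P(positive) = Σ over x = 1 to 18 of Bin(x; 18, p) × P(Bin(14, p) ≥ r + 1 − x)

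Equivalently, take the single-stage probability and subtract the paths that would have stopped at stage 1:

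P(positive) = P(Bin(32, p) ≥ r + 1) − (1 − p)^18 × P(Bin(14, p) ≥ r + 1)

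**Step 1: the plan's stage 1 figure.** 0.95^18 = 0.397, which matches the stated 40%. The stage 1 part is correct and does not depend on r.

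**Step 2: operating characteristics of the two final rules.**

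| Rule | p | Single-stage term | Subtracted term | P(positive) |
|---|---|---|---|---|
| r = 4 (17.1, synopsis) | 0.05 | 0.0204 | 0.0002 | **0.0202** |
| r = 4 | 0.20 | 0.7956 | 0.0023 | **0.7933** |
| r = 3 (5.2) | 0.05 | 0.0738 | 0.0017 | **0.0721** |
| r = 3 | 0.20 | 0.9069 | 0.0054 | **0.9015** |

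With r = 4 the type II error is 1 − 0.7933 = 0.207. With r = 3 it is 1 − 0.9015 = 0.099. The stated 90% power is reproduced by r = 3 and not by r = 4.

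**Step 3: which design do the inputs imply?** A search over total size, stage 1 size and both boundaries, for type I error at most 0.10 and power at least 0.90, returns stop at 0 of 18, negative at 3 or fewer of 32. Its early stopping probability is 0.397 and its expected sample size under the null is 18 + 14 × (1 − 0.397) = 26.4. Every stated parameter fits r = 3. The boundary of 4 is the only element that does not.

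**Step 4: can any reading give r = 4 a power of 90%?**

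- No interim look, single stage with n = 32: 0.796. A futility stop can only lower power, so no stage 1 rule reaches 90% with at least 5 of 32.
- All 35 planned patients analysed, boundaries unchanged: 0.852.
- Keeping the stage 1 rule and raising total n: 0.895 at 38 and 0.906 at 39, so 39 patients would be needed.

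**Step 5: how likely is the disputed result?** This is the probability of passing stage 1 and ending with exactly 4 responses, which is the difference between the two rules.

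| True rate | r = 3 positive | r = 4 positive | Exactly 4 |
|---|---|---|---|
| 5% | 7.2% | 2.0% | 5.2% |
| 10% | 39.3% | 21.0% | 18.3% |
| 20% | 90.1% | 79.3% | 10.8% |

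**The case against.** **The stated type I error is not breached.** In a Simon design 0.10 is a ceiling, and 0.020 satisfies it. Only the power statement fails, and the error is conservative for false positives. This stands.

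**The intended rule is not documented.** The boundary of 4 is in the dedicated statistical section and the synopsis, and the boundary of 3 appears once. At least 5 also agrees with the planned 95% interval: for 5 of 32 the exact lower limit is about 5.3%, which excludes the 5% null, while for 4 of 32 it is 3.5%, which does not. A sponsor could have wanted the stricter bar. That is possible, but such a sponsor could not also claim 90% power, and the minimax label with 18 and 32 fits only the boundary of 3.

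**Adopting 3 lowers the bar for success.** The synopsis gives the reference response rate as 5 to 10%. At a true rate of 10%, the chance of a positive trial rises from 21.0% to 39.3%. This is a real cost, and the sponsor should see it when choosing.

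**The figures assume exactly 32 patients.** Section 17.2 counts every dosed patient as evaluable and 35 are planned. With 35 analysed and boundaries unchanged, r = 4 gives type I error 0.029 and power 0.852, and r = 3 gives 0.092 and 0.931. The power shortfall with r = 4 narrows from about 11 points to about 5 but does not close.

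**Conclusion.** The concern holds. The protocol contains two incompatible final decision rules for its primary endpoint, and the one in Section 17.1 and the synopsis has 79.3% power at a 20% response rate against the stated 90%. Its type II error is 20.7%, about double the stated 10%. Its type I error of 2.0% is within the limit. The rule in Section 5.2 meets both limits (7.2% and 90.1%) and is the minimax design for the stated inputs.

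These figures assume independent binomial responses, 18 and 32 patients analysed, and the stage 1 stop applied as written. This must be corrected, because the contradiction decides whether a realistic result counts as success or failure.

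**What to change.** State one final boundary in Section 5.2, Section 17.1 and the synopsis, with its exact operating characteristics, before the final response data are known.

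- **Preferred, because it fits the stated design:** in Section 17.1 and the synopsis, make 3 or fewer responses among 32 negative and 4 or more positive. Give type I error 0.072 and power 0.901.
- **If the stricter bar is intended:** keep at least 5 of 32 for a positive result, correct Section 5.2, and restate type I error as 0.020 and power as 79%.

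Either choice changes wording only and adds no patients. The first raises the chance of a positive trial from 2.0% to 7.2% at a true rate of 5%, still under the planned 10%, and from 21.0% to 39.3% at 10%. The second accepts a 20.7% chance of missing a drug with the target rate.

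Optionally, if the boundary of 3 is adopted, report a one-sided 90% lower bound beside the planned 95% interval. At 4 of 32 the exact 95% interval is 3.5% to 29.0% and includes the null, while the one-sided 90% lower bound is 5.6%. Both ignore the two-stage sampling, so they describe the result and the boundary decides it.
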